11. MEASUREMENT OF EFFECT

11.1 Antitumor Effect – Solid Tumors

For the purposes of this study, participants should be re-evaluated for response every 2 cycles of treatment or approximately every 6 weeks.

Response and progression will be evaluated in this study using the new international criteria proposed by the Response Evaluation Criteria in Solid Tumors (RECIST) guideline (version 1.1) [Eur J Ca 45:228-247, 2009]. Changes in the largest diameter (unidimensional measurement) of the tumor lesions and the shortest diameter in the case of malignant lymph nodes are used in the RECIST criteria.

11.1.1 Definitions

Evaluable for Target Disease response. Only those participants who have measurable disease present at baseline, have initiated study treatment, and have had their disease revaluated will be considered evaluable for target disease response. These participants will have their response classified according to the definitions stated below. (Note: Participants who exhibit objective disease progression prior to the end of cycle 1 will also be considered evaluable.)

Evaluable Non-Target Disease Response. Participants who have lesions present at baseline that are evaluable but do not meet the definitions of measurable disease, have received at least one cycle of therapy, and have had their disease re-evaluated will be considered evaluable for non-target disease. The response assessment is based on the presence, absence, or unequivocal progression of the lesions.

11.1.2 Disease Parameters

Measurable disease. Measurable lesions are defined as those that can be accurately measured in at least one dimension (longest diameter to be recorded) as ≥ 20 mm by chest x-ray or ≥ 10 mm with CT scan, MRI, or calipers by clinical exam. All tumor measurements must be recorded in millimeters (or decimal fractions of centimeters).

Note: Tumor lesions that are situated in a previously irradiated area might be considered measurable if the investigator thinks it appropriate to include them.

Malignant lymph nodes. To be considered pathologically enlarged and measurable, a lymph node must be ≥ 15 mm in short axis when assessed by CT scan (CT scan slice thickness recommended to be no greater than 5 mm). At baseline and in follow-up, only the short axis will be measured and followed.

Non-measurable disease. All other lesions (or sites of disease), including small lesions

(longest diameter <10 mm or pathological lymph nodes with ≥10 to <15 mm short axis), are considered non-measurable disease. Bone lesions, leptomeningeal disease, ascites, pleural/pericardial effusions, lymphangitis cutis/pulmonitis, inflammatory breast disease, abdominal masses (not followed by CT or MRI), and cystic lesions are all considered non-measurable.

Note: Cystic lesions that meet the criteria for radiographically defined simple cysts should not be considered as malignant lesions (neither measurable nor non-measurable) since they are, by definition, simple cysts.

'Cystic lesions' thought to represent cystic metastases can be considered as measurable lesions, if they meet the definition of measurability described above. However, if non-cystic lesions are present in the same participant, these are preferred for selection as target lesions.

Target lesions. All measurable lesions up to a maximum of 2 lesions per organ and 5 lesions in total, representative of all involved organs, should be identified as **target lesions** and recorded and measured at baseline. Target lesions should be selected on the basis of their size (lesions with the longest diameter), be representative of all involved organs, but in addition should be those that lend themselves to reproducible repeated measurements. It may be the case that, on occasion, the largest lesion does not lend itself to reproducible measurement in which circumstance the next largest lesion which can be measured reproducibly should be selected. A sum of the diameters (longest for non-nodal lesions, short axis for nodal lesions) for all target lesions will be calculated and reported as the baseline sum diameters. If lymph nodes are to be included in the sum, then only the short axis is added into the sum. The baseline sum diameters will be used as reference to further characterize any objective tumor regression in the measurable dimension of the disease.

Non-target lesions. All other lesions (or sites of disease) including any measurable lesions over and above the 5 target lesions should be identified as **non-target lesions** and should also be recorded at baseline. Measurements of these lesions are not required, but the presence, absence, or in rare cases unequivocal progression of each should be noted throughout follow up.

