3. PARTICIPANT SELECTION

3.1 Inclusion Criteria

- 3.1.1 Participants must have histologically or cytologically confirmed invasive breast cancer, with either locally advanced or metastatic disease. Patients without pathologic or cytologic confirmation of metastatic disease should have unequivocal evidence of metastasis from physical examination or radiologic evaluation.
- 3.1.2 Either the primary invasive tumor and/or the metastasis must be triple-negative, defined as:
 - hormone-receptor poor, ER- and PR-negative, or staining present in <1% by immunohistochemistry (IHC)
 - HER2-negative: 0 or 1+ by IHC, or FISH<2.0

- 3.1.3 Participants must have at least one lesion that is not within a previously radiated field that is measurable on computerized tomography (CT) or magnetic resonance imaging (MRI) scan per RECIST version 1.1. Bone lesions are not considered measurable by definition. See Section 11 for the evaluation of measurable disease.
- 3.1.4 Prior chemotherapy: Patients may have received 0-1 prior chemotherapeutic regimen for metastatic breast cancer and must have been off treatment with chemotherapy for at least 21 days before enrollment in the study. The number of patients with 0 prior chemotherapeutic regimen will be limited to a maximum of n = 20.
- 3.1.5 Prior biologic therapy: Patients must have discontinued all biologic therapy at least 21 days before participation.
- 3.1.6 Prior radiation therapy: Patients may have received prior radiation therapy in either the metastatic or early-stage setting. Radiation therapy must be completed at least 14 days prior to study participation and patients should have recovered from adverse effects of radiation to grade ≤1.
- 3.1.7 Age ≥ 18
- 3.1.8 ECOG performance status ≤1
- 3.1.9 Participants must have normal organ and marrow function as defined below:
 - Absolute neutrophil count ≥1500/mm³
 - Platelets $\geq 100.000/\text{mm}^3$
 - Hemoglobin ≥9 g/dL
 - Total Bilirubin ≤1.5 mg/dL
 - Serum creatinine ≤1.5 mg/dL OR measured creatinine clearance (CrCl) ≥45 mL/min as calculated by the Cockcroft-Gault method OR 24-hour measured urine CrCl ≥45mL/min
 - Alanine aminotransferase (ALT) and aspartate aminotransferase (AST) ≤2.5 times the upper limit of normal. For patients with documented liver metastases, AST/ALT ≤ 5.0 times the upper limit of normal.

- 3.1.10 Patients on bisphosphonates may continue receiving bisphosphonate therapy during study treatment.

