11.1.3 Methods for Evaluation of Disease

All measurements should be taken and recorded in metric notation using a ruler, calipers, or a digital measurement tool. All baseline evaluations should be performed as closely as possible to the beginning of treatment and never more than 4 weeks before the beginning of the treatment.

The same method of assessment and the same technique should be used to characterize each identified and reported lesion at baseline and during follow-up. Imaging-based evaluation is preferred to evaluation by clinical examination unless the lesion(s) being followed cannot be imaged but are assessable by clinical exam.

Clinical lesions. Clinical lesions will only be considered measurable when they are superficial (e.g., skin nodules and palpable lymph nodes) and ≥ 10 mm in diameter as assessed using calipers (e.g., skin nodules). In the case of skin lesions, documentation by color photography, including a ruler to estimate the size of the lesion, is recommended.

Chest x-ray. Lesions on chest x-ray are acceptable as measurable lesions when they are clearly defined and surrounded by aerated lung; however, CT is preferable.

Conventional CT and MRI. This guideline has defined measurability of lesions on CT scan based on the assumption that CT thickness is 5mm or less. If CT scans have slice thickness greater than 5 mm, the minimum size of a measurable lesion should be twice the slice thickness. MRI is also acceptable in certain situations (*e.g.* for body scans).

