11.1.4 Response Criteria

11.1.4.1 Evaluation of Target Lesions

Complete Response (CR): Disappearance of all target lesions. Any pathological lymph nodes (whether target or non-target) must have reduction in short axis to <10 mm.

Partial Response (PR): At least a 30% decrease in the sum of the diameters of target lesions, taking as reference the baseline sum diameters.

Progressive Disease (PD): At least a 20% increase in the sum of the diameters of target lesions, taking as reference the smallest sum on study (this includes the baseline sum if that is the smallest on study). In addition to the relative increase of 20%, the sum must also demonstrate an absolute increase of at least 5 mm. (Note: the appearance of one or more new lesions is also considered progressions).

Stable Disease (SD): Neither sufficient shrinkage to qualify for PR nor sufficient increase to qualify for PD, taking as reference the smallest sum diameters while on study.

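### Previously irradiated lesions can enter the target sum without proof of growth since radiotherapy, and no rule places the baseline scan after radiotherapy, so radiation shrinkage can contribute to a partial response.

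*Combined protocol and SAP*

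**What the plan says.** Five rules bear on this point.

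- **Eligibility (3.1.3):** "Participants must have at least one lesion that is not within a previously radiated field that is measurable" on CT or MRI.
- **Measurability (11.1.2, note under measurable disease):** "Tumor lesions that are situated in a previously irradiated area might be considered measurable if the investigator thinks it appropriate to include them". No condition is attached.
- **Target lesions (11.1.2):** "All measurable lesions up to a maximum of 2 lesions per organ and 5 lesions in total" are to be taken as targets, with size as a main criterion. For the resulting sum, "The baseline sum diameters will be used as reference to further characterize any objective tumor regression". PR in 11.1.4.1 is "At least a 30% decrease in the sum of the diameters of target lesions".
- **Prior radiotherapy (3.1.6):** "Radiation therapy must be completed at least 14 days prior to study participation". Study participation is not defined.
- **Baseline imaging (11.1.3; Section 10 sets the same limit):** the outer limit for the scan is "never more than 4 weeks before the beginning of the treatment". Within that limit 11.1.3 states a preference for late timing: "All baseline evaluations should be performed as closely as possible to the beginning of treatment". Neither place mentions the end of radiotherapy.

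ORR by RECIST 1.1 is the primary endpoint (13.2). The single arm is judged against a fixed 20% null with a two-stage rule: at least 4 responses in 17 to continue, and at least 11 in 37 for success (13.1).

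**The concern.** There are two separate openings.

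The first is the note in 11.1.2. A lesion irradiated shortly before entry may still be regressing when it is measured at baseline. If the investigator counts it as measurable, its later shrinkage enters the sum on the same footing as shrinkage caused by the study drugs. Section 3.1.3 secures one clean lesion per patient, but it is an eligibility rule and does not govern which lesions make up the sum.

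The second is scan timing. Nothing prevents the baseline measurement from being made before radiotherapy to that lesion is complete. The reference diameter would then include tumour that radiation goes on to remove.

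In a randomised comparison such effects would tend to appear in both arms. Here there is no control arm, lesion choice rests with an investigator who knows the treatment, and the decision turns on 10 versus 11 responders. The central review in 11.1.7 carries no rule on irradiated lesions, so it would apply the same permission. The provision on palliative radiation in 5.4 concerns radiation during the study, not before it.

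**Working it through.** **1. The plan's own figures.** Inputs from 13.1: 17 patients in stage 1, continue with 4 or more responses; 20 more patients, success with 11 or more of 37.

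P(success | p) = sum over x = 4 to 17 of Bin(17, x, p) × P(Bin(20, p) ≥ 11 − x)

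- p = 0.20: 0.0948 (stated 0.095)
- p = 0.40: 0.9033 (stated 0.903)

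Both reproduce.

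**2. How far the scan can precede the end of radiotherapy.** Suppose study participation begins g days before cycle 1 day 1. Radiotherapy must then end at least 14 + g days before treatment. The scan may be up to 28 days before treatment. The largest gap is 28 − (14 + g) = 14 − g days.

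- g = 0: up to 14 days
- g = 7: up to 7 days
- g ≥ 14: none

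The value of g is not in the documents.

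**3. Shrinkage of the irradiated lesion that alone gives a PR.** Let u be the unirradiated diameter, unchanged, and i the irradiated diameter. The fraction of i that must be lost is 0.30 × (u + i) / i.

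| u (mm) | i (mm) | Calculation | Loss needed in i |
|---|---|---|---|
| 15 | 40 | 0.30 × 55 / 40 | 41% |
| 20 | 40 | 0.30 × 60 / 40 | 45% |
| 15 | 30 | 0.30 × 45 / 30 | 45% |
| 20 | 30 | 0.30 × 50 / 30 | 50% |

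Worked case: 15 + 40 = 55 mm at baseline and 15 + 22 = 37 mm at follow-up. The change is 1 − 37/55 = 32.7%, a PR with no change in the only unirradiated lesion.

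**4. How fragile that case is.** PR needs a sum of at most 0.70 × 55 = 38.5 mm. With the irradiated lesion at 22 mm, the other may reach at most 16.5 mm, which is 1.5 mm of growth. At 18 mm the sum is 40 mm, the fall is 1 − 40/55 = 27.3%, and the result is stable disease.

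**5. Effect on the decision rule, illustration only.** Assume a true response rate of 20% and a counted rate raised by k responders per 37.

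| k | Counted rate | P(success) |
|---|---|---|
| 0 | 0.200 | 0.095 |
| 0.5 | 0.20 + 0.5/37 = 0.2135 | 0.135 |
| 1 | 0.20 + 1/37 = 0.227 | 0.184 |

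The values of k are assumptions; nothing in the documents yields them.

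**The case against.** The best case on the other side is that this is a rare situation, already hedged by several rules.

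- **Study participation is undefined.** Neighbouring criteria count from enrollment, first dose or start of treatment, so it need not mean day 1. If it begins at consent, which the calendar places before any study-specific procedure, a baseline scan performed for the protocol follows the end of radiotherapy by at least 14 days. A reader might infer that any site may scan on day −28, finish radiotherapy on day −14 and keep the old scan. The text supports that only if participation is at or near day 1, and even then the practice sits badly with the instruction to scan as close to treatment as possible. This objection stands: the timing gap is conditional.
- **The note does not create the timing gap.** A lesion scanned before radiation is not yet in an irradiated area. This also stands, and it is why the two openings need two separate sentences in the fix.
- **Response must be confirmed.** The table in 11.1.4.4 asks for confirmation at 4 weeks or more and allows no new lesions and no non-target progression. This removes transient shrinkage and patients whose other disease grows. It does not remove lasting radiation shrinkage beside a nearly static lesion.
- **Few lesions qualify.** Bone lesions cannot be targets, and treated brain metastases need at least a month without progression (3.2.5). What remains is recent radiotherapy to other measurable disease. A complete response from radiation alone is not a realistic concern, because the unirradiated disease would also have to disappear.
- **Direction.** A reader might infer that the note can only raise the ORR. The documents do not show that. The note covers radiation at any time, and an old inert lesion would add fixed millimetres to the sum and make PR harder. Whether the studies behind the 20% null used the same convention cannot be seen. The upward direction is clear only for recently irradiated lesions that are still shrinking, or that were scanned before radiotherapy ended.

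**Conclusion.** The measurement rules allow shrinkage from prior radiotherapy to contribute to a PR and, where the unirradiated lesion stays nearly static, to produce one alone, even with confirmation. The first opening, the unconditional note, rests on the text as it stands and on the premise that a recently irradiated lesion may still be regressing; the documents give no figure for that. The second, a baseline scan before the end of radiotherapy, depends on what study participation means: the overlap is up to 14 − g days, and none if g is 14 or more.

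The effect on the trial's error rate cannot be determined. A reader might take 0.184 as the real type I error. It is not: it is what follows if one extra responder per 37 is assumed, and the documents do not give the number of patients with recent radiotherapy to a lesion that could be a target. The stated 0.095 is correctly computed. The figures show only that the rule is sensitive to a single responder.

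This is a cheap improvement to the definition of the primary endpoint, not a defect in the design.

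**What to change.** **In 11.1.2**, replace the note: a lesion in a previously irradiated area may be a target lesion only if growth has been documented on imaging after radiotherapy; otherwise it is recorded as non-target.

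**In Section 10 and 11.1.3**, add that the baseline tumour scan must be taken after the last radiotherapy dose and within the existing 4-week window. For this purpose the meaning of study participation then no longer matters.

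**Cost.** The first change makes no patient ineligible, because 3.1.3 already guarantees a measurable lesion outside any radiated field. The second always fits the window if participation begins no later than day 1, since 3.1.6 then leaves at least 14 days between the end of radiotherapy and treatment. The downside is a later screening scan or, for a few patients already scanned, a repeat one.

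**If accrual has begun**, report a sensitivity ORR with irradiated lesions removed from the target sum. Where the unirradiated lesion was not chosen as a target, it would have to be measured from the stored scans.

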11.1.3 Methods for Evaluation of Disease

All measurements should be taken and recorded in metric notation using a ruler, calipers, or a digital measurement tool. All baseline evaluations should be performed as closely as possible to the beginning of treatment and never more than 4 weeks before the beginning of the treatment.

The same method of assessment and the same technique should be used to characterize each identified and reported lesion at baseline and during follow-up. Imaging-based evaluation is preferred to evaluation by clinical examination unless the lesion(s) being followed cannot be imaged but are assessable by clinical exam.

Clinical lesions. Clinical lesions will only be considered measurable when they are superficial (e.g., skin nodules and palpable lymph nodes) and ≥ 10 mm in diameter as assessed using calipers (e.g., skin nodules). In the case of skin lesions, documentation by color photography, including a ruler to estimate the size of the lesion, is recommended.

Chest x-ray. Lesions on chest x-ray are acceptable as measurable lesions when they are clearly defined and surrounded by aerated lung; however, CT is preferable.

Conventional CT and MRI. This guideline has defined measurability of lesions on CT scan based on the assumption that CT thickness is 5mm or less. If CT scans have slice thickness greater than 5 mm, the minimum size of a measurable lesion should be twice the slice thickness. MRI is also acceptable in certain situations (*e.g.* for body scans).

Use of MRI remains a complex issue. MRI has excellent contrast, spatial, and temporal resolution; however, there are many image acquisition variables involved in MRI, which greatly impact image quality, lesion conspicuity, and measurement. Furthermore, the availability of MRI is variable globally. As with CT, if an MRI is performed, the technical specifications of the scanning sequences used should be optimized for the evaluation of the type and site of disease. Furthermore, as with CT, the modality used at follow-up should be the same as was used at baseline and the lesions should be measured/assessed on the same pulse sequence. It is beyond the scope of the RECIST guidelines to prescribe specific MRI pulse sequence parameters for all scanners, body parts, and diseases. Ideally, the same type of scanner should be used and the image acquisition protocol should be followed as closely as possible to prior scans. Body scans should be performed with breath-hold scanning techniques, if possible.

FDG-PET. While FDG-PET response assessments need additional study, it is sometimes reasonable to incorporate the use of FDG-PET scanning to complement CT scanning in assessment of progression (particularly possible 'new' disease). New lesions on the basis of FDG-PET imaging can be identified according to the following algorithm:

- (a) Negative FDG-PET at baseline, with a positive FDG-PET at follow-up is a sign of PD based on a new lesion.
- (b) No FDG-PET at baseline and a positive FDG-PET at follow-up: If the positive FDG-PET at follow-up corresponds to a new site of disease confirmed by CT, this is PD. If the positive FDG-PET at follow-up is not confirmed as a new site of disease on CT, additional follow-up CT scans are needed to determine if there is truly progression occurring at that site (if so, the date of PD will be the date of the initial abnormal FDG-PET scan). If the positive FDG-PET at follow-up corresponds to a pre-existing site of disease on CT that is not progressing on the basis of the anatomic images, this is not PD.
- (c) FDG-PET may be used to upgrade a response to a CR in a manner similar to a biopsy in cases where a residual radiographic abnormality is thought to represent fibrosis or scarring. The use of FDG-PET in this circumstance should be prospectively described in the protocol and supported by disease-specific medical literature for the indication. However, it must be acknowledged that both approaches

may lead to false positive CR due to limitations of FDG-PET and biopsy resolution/sensitivity.

Note: A 'positive' FDG-PET scan lesion means one which is FDG avid with an uptake greater than twice that of the surrounding tissue on the attenuation corrected image.

PET-CT. At present, the low dose or attenuation correction CT portion of a combined PET-CT is not always of optimal diagnostic CT quality for use with RECIST measurements. However, if the site can document that the CT performed as part of a PET-CT is of identical diagnostic quality to a diagnostic CT (with IV and oral contrast), then the CT portion of the PET-CT can be used for RECIST measurements and can be used interchangeably with conventional CT in accurately measuring cancer lesions over time. Note, however, that the PET portion of the CT introduces additional data which may bias an investigator if it is not routinely or serially performed.

MIBG (meta-iodobenzylguanidine). The following is recommended, to assure high quality images are obtained.

Patient preparation: Iodides, usually SSKI (saturated solution of potassium iodide), are administered to reduce thyroidal accumulation of free radioiodine, preferably beginning the day prior to injection and continuing for 3 additional days (4 days total). For adults 3 drops t.i.d. Participants are asked about exposure to potential interfering agents. If none is noted, an indwelling intravenous line is established. The dose of MIBG is administered by slow intravenous injection over 90 seconds.

Images from the head to the distal lower extremities should be obtained.

I-123MIBG scintigraphy is performed to obtain both planar and tomographic images.

Planar: Anterior and posterior views from the top of the head to the proximal lower extremities are obtained for 10 minutes at 24 hours and occasionally at 48 hours following injection of 10 mCi/1.7 square meters of body surface area (\sim 150 μ Ci/kg, maximum 10 mCi). Anterior views of the distal lower extremities are adequate. A large field of view dual head gamma camera with low energy collimators is preferred.

SPECT: Most participants receiving I-123 MIBG also undergo SPECT at 24 hours, using a single or multi-headed camera with a low energy collimator. The camera is rotated through 360 degrees, 120 projections at 25 seconds per stop. Data are reconstructed using filtered back projections with a Butterworth filter and a cut off frequency of 0.2-0.5. SPECT/CT may be performed at institutions with this capacity.

Ultrasound. Ultrasound is not useful in assessment of lesion size and should not be used as a method of measurement. Ultrasound examinations cannot be reproduced in their entirety for independent review at a later data and, because they are operator dependent, it

cannot be guaranteed that the same technique and measurements will be taken from one assessment to the next. If new lesions are identified by ultrasound in the course of the study, confirmation by CT or MRI is advised. If there is concern about radiation exposure from CT, MRI may be used instead of CT in selected instances.

Endoscopy, Laparoscopy. The utilization of these techniques for objective tumor evaluation is not advised. However, such techniques may be useful to confirm complete pathological response when biopsies are obtained or to determine relapse in trials where recurrence following complete response (CR) or surgical resection is an endpoint.

Tumor markers. Tumor markers alone cannot be used to assess response. If markers are initially above the upper normal limit, they must normalize for a participant to be considered in complete clinical response. Specific guidelines for both CA-125 response (in recurrent ovarian cancer) and PSA response (in recurrent prostate cancer) have been published [*JNCI* 96:487-488, 2004; *J Clin Oncol* 17, 3461-3467, 1999; *J Clin Oncol* 26:1148-1159, 2008]. In addition, the Gynecologic Cancer Intergroup has developed CA-125 progression criteria which are to be integrated with objective tumor assessment for use in first-line trials in ovarian cancer [*JNCI* 92:1534-1535, 2000].

Cytology, Histology. These techniques can be used to differentiate between partial responses (PR) and complete responses (CR) in rare cases (*e.g.*, residual lesions in tumor types, such as germ cell tumors, where known residual benign tumors can remain).

The cytological confirmation of the neoplastic origin of any effusion that appears or worsens during treatment when the measurable tumor has met criteria for response or stable disease is mandatory to differentiate between response or stable disease (an effusion may be a side effect of the treatment) and progressive disease.

